### Sample size and power

This is a pilot RCT, and the primary outcomes of this study are: 1) to test the feasibility and acceptability of the crowdsourced intervention, and 2) to pilot the preliminary impact of crowdsourced PS intervention in promoting HIV testing among partners of the newly identified HIV cases. In addition, this pilot RCT aimed to collect preliminary data for the designing of a full RCT, which aimed to measure the efficacy of the crowdsourced PS intervention in promoting PS. Thus, the sample size of this study is not designed and will be not powered enough to test the difference between the two arms. However, with a sample size of 120 (80 for intervention arm and 40 for the control arm, respectively), this pilot study would collect enough information to measure the feasibility and acceptability of the intervention, and it will be able to observe the differences between the two arms and collect preliminary data for an adequate sample size calculation of a full RCT. With a sample size of 120 (ratio of 2:1), alpha=0.05, power=0.80, and the partner return rate in the conventional PS arm is 30% (around 31% in 2016 in Guangzhou), the minimal detectable effect size would be 26.7% for this pilot study.

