## Statistical Analysis Plan

For the primary outcomes of feasibility and acceptability of the intervention: this will be analyzed through descriptive analysis to assess the feedback on the feasibility and acceptability of the crowdsourced PS intervention among index MSM and their partners in the intervention group. For the primary outcome of the proportion of partners returning for HIV testing within 3 months of the index participant's enrolment in the study, log-binomial regression (generalized linear model with binomial distribution and log link) will be used to calculate 95% confidence intervals for the proportion of notifiable partners visiting by arm. Risk differences and risk ratios will also be calculated in these models. As this study is a pilot RCT, and we will only recruit 120 index MSM, and they will be randomly assigned in a 2:1 ratio, adjustment for covariates would be necessary if the two study arms are not balanced. In secondary analyses, we will adjust for pre-specified potential confounding variables that might bias the estimate if not accounted for (e.g. index age, index marital status). If a partner reports more than one index referred him, he will be counted as a returning partner for each identified index.

*Table 1* Analysis strategies for secondary outcomes

Secondary Outcome	Population	Model Type
The proportion of reported partners being notified by indexes among all reported partners	Reported sexual partners	Binomial regression, robust variance
Mean number of partners tested per index participant	Index participants	Poisson or negative binomial regression, robust variance
The proportion of positive HIV tests among tested partners	Tested sexual partners	Binomial regression, robust variance
Mean number of partners with HIV (case-finding) per index participant	Index participants	Poisson or negative binomial regression, robust variance
The proportion of reported partners getting HIV testing who are not spouses or regular partners	Reported casual male sexual partners	Binomial regression, robust variance
The proportion of presenting partners reporting condom use during the last anal intercourse	Presenting sexual partners	Binomial regression, robust variance

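### The SAP gives no method for a single covariate-adjusted risk difference, no fallback if the log-binomial fit fails, and no variance grouped by index for the partner-testing outcome

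*Combined protocol and SAP*

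**What the plan says.** The Statistical Analysis Plan section names a single model for the comparative primary outcome, partners tested within three months of the index participant's enrolment: "log-binomial regression (generalized linear model with binomial distribution and log link) will be used to calculate 95% confidence intervals" for the proportion in each arm. The next sentence reads "Risk differences and risk ratios will also be calculated in these models".

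Covariates come only after that. The plan says "adjustment for covariates would be necessary if the two study arms are not balanced", and then "In secondary analyses, we will adjust for pre-specified potential confounding variables that might bias the estimate if not accounted for". Index age and index marital status are given as examples.

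The section names no identity link, no step that turns an adjusted log-link fit into one risk difference, and no alternative model if the fit does not converge. Table 1 specifies robust variance for all six secondary outcomes; the text on the primary testing outcome does not mention it. The binomial rows of Table 1 do not name a link.

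The Sample size and power section says that the pilot is not powered for the comparison between arms. It gives a detectable difference of 26.7% under these conditions: "With a sample size of 120 (ratio of 2:1), alpha=0.05, power=0.80", with 80 and 40 index participants and a 30% control rate.

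**The concern.** A log link holds the risk ratio constant across covariate values, so the risk difference cannot also be constant. With arm alone this does no harm. Once age or marital status enters, every covariate pattern has its own implied difference, and the plan does not say which one, or which average, is to be reported. Two analysts could follow the text faithfully and publish different adjusted differences from the same fit.

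The log link also does not keep fitted risks below 1. Estimation can therefore fail to converge or end with a fitted risk at or above 1. With no fallback named, the replacement would be chosen after the data had been seen.

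A separate gap affects the unadjusted interval too. The unit of analysis is the partner, but randomisation is of index participants. If partners of the same index behave alike, a binomial standard error that treats them as independent is too small. In a pilot that is not powered to test the difference, the estimate and its interval are the main comparative product.

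**Working it through.** **1. The plan's own figure.** Inputs from the Sample size and power section: 40 control, 80 intervention, 30% against 56.7%, alpha 0.05 (two-sided assumed).

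- Pooled proportion = (40×0.30 + 80×0.567)/120 = 0.478.
- Null SE = √[0.478×0.522×(1/40 + 1/80)] = 0.0967.
- Alternative SE = √[0.30×0.70/40 + 0.567×0.433/80] = 0.0912.
- z = (0.267 − 1.96×0.0967)/0.0912 = 0.85, so power is 0.802.

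The 26.7-point figure reproduces, and nothing below changes it.

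**2. Arm-only model.** Take 12/40 against 45/80. The model is saturated, so exp(b0) = 0.30 and exp(b0 + b1) = 0.5625. Their difference is 0.2625, which equals 45/80 − 12/40. In simulation this model failed in 0% of data sets in every scenario.

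**3. Adjusted model: no single risk difference.** With a constant risk ratio, RD = p0×(RR − 1). The planning rates give RR = 0.567/0.30 = 1.89.

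| Baseline risk p0 | RD at RR 1.89 | RD at RR 1.5 |
|---|---|---|
| 15% | 13.35 points | 7.5 points |
| 30% | 26.7 points | 15 points |
| 50% | 44.5 points | 25 points |

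At RR 1.89, a control risk above 1/1.89 = 53% for any covariate pattern implies an intervention risk above 1.

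**4. Adjusted model: failure of the fit.** The documents give neither covariate effects nor the number of partners per index, so all of the following is assumed: standardised age, 15% married, one partner or a mean of three per index, 30% control rate, 400 simulated trials per cell. Failure means non-convergence, a non-finite standard error, or a fitted risk of 1 or more. Each cell shows one partner / mean of three.

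| Covariate effects | 40% intervention | 50% intervention | 56.7% intervention |
|---|---|---|---|
| None | 1.5% / 0% | 5.75% / 0% | 8.5% / 0.25% |
| Moderate (OR 1.3 per SD of age, 1.5 married) | 15.25% / 2.75% | 24.5% / 4.25% | 30.5% / 11% |
| Strong (OR 1.7 and 2) | 57% / 41% | 68% / 56% | 70% / 65% |

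Repeat runs with no, moderate and strong effects gave 0–1%, 4–14% and 35–58%.

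**5. Standardisation from a logistic model.** In the data sets of step 4, fitting a logistic model and averaging predicted risks with every partner set to each arm gave one adjusted difference in 100% of trials. Means were 0.095–0.103, 0.188–0.204 and 0.254–0.272 for intervention rates of 40%, 50% and 56.7%. Two limits apply. The data were generated from a logistic model, which favours this method, and they carried no within-index correlation beyond the shared covariates.

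**6. Grouping by index.** With an assumed index effect of SD 1, the arm-only standard error grouped by index was 23–31% larger than the ungrouped one. Under a normal approximation, a nominal 95% interval that ignores this covers 2Φ(1.96/1.23) − 1 = 89% down to 2Φ(1.96/1.31) − 1 = 87%.

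**The case against.** The sentence on risk differences follows directly after the by-arm model and precedes any mention of covariates. The plan never promises an adjusted risk difference. The adjusted risk ratio is a direct parameter of the model, and a single marginal difference can be had from a log-binomial fit by averaging predicted risks, a step the plan omits but does not exclude. The failure rates depend on covariate effects that nobody knows yet. The study is a pilot, and the unadjusted proportions are enough to help size the later trial.

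Most of this stands. A reader might infer that the primary effect estimate is wrong or may be unobtainable; the documents do not support that, because the main analysis as described has no covariates and step 2 shows it is exact. A reader might also infer that the model will usually break down; the documents hold no figure from which to say so. Nor is the adjusted risk ratio invalid when the fit succeeds.

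The obvious replacement, modified Poisson regression, is also not a full cure. It avoids non-convergence but uses the same unbounded log link, and in comparable simulations it gave fitted values of 1 or more in 0–60% of trials. It is a poor basis for averaged risks.

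Three things remain. The adjusted analysis is planned, and the wording that adjustment is necessary under imbalance leaves its standing unclear. For that analysis neither a single difference nor a fallback is defined. And the omission of robust variance reaches the primary interval itself.

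**Conclusion.** The point holds in a limited form. The unadjusted risk difference and risk ratio are sound as point estimates.

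For the adjusted analysis of partner testing, labelled secondary, the plan leaves the risk difference undefined: 13.35 to 44.5 points over baseline risks of 15% to 50% at a risk ratio of 1.89. It also names no alternative if the fit fails. The chance of failure runs from about 0% to 60–70% across the assumed scenarios and cannot be narrowed from the documents.

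Intervals, including the unadjusted one, do not account for partners nested within index participants. The 23–31% larger standard error rests on an assumed index effect and shows only that the omission can matter.

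This is worth correcting before analysis because the correction is cheap. It does not threaten the trial's main comparative estimates.

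**What to change.** - Keep the arm-only log-binomial point estimates.
- Use variance grouped by index participant for every partner-level interval, unadjusted and adjusted. The SAP counts a partner referred by two indexes under both; grouping by index does not capture that overlap, and the documents give no count of such partners.
- For the adjusted analysis, list the covariates in full and fit a logistic model with arm and those covariates. Average the predicted risks with all partners set to each arm, and report the difference and the ratio of the two averages. Give an index-level bootstrap or a cluster-robust delta-method interval. Predicted risks then stay below 1.
- Modified Poisson with variance grouped by index may serve as a check on the risk ratio only.
- In Table 1, state the link for the binomial rows; no change of model is needed there on this account.

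The cost is SAP wording and a few lines of code. The adjusted risk ratio becomes marginal rather than conditional, which the report should say.

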## **Randomization**

Eligible participants will be randomly assigned to the crowdsourced PS arm (intervention arm) or conventional PS (control arm) in a 2:1 ratio. Since information under the control situation is already available from Guangzhou, a 2:1 ratio will allow us to spend more resources on intervention, and collect more primary outcome relevant data from participants in the intervention group (especially for the measure of the feasibility and acceptability). This approach ensures that the index participants in each arm will be evenly distributed. The number of partners

may vary somewhat across the two arms, as the number of partners of the index participants is variable. However, the total number of partners in the two arms should be comparable.

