## **Additional measures**

In addition to the primary and secondary outcomes, we will collect index and presenting partners' socio-demographics, sexual orientation, sexual orientation disclosure status, HIV and other STDs testing history and HIV PS history.

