Subgroup analyses will be performed by partner type (e.g. main male partner vs. casual male partner). For secondary outcomes, analysis approaches are provided in Table 1. For count variables expressed as the mean number of partners, we will use either Poisson regression or negative binomial regression if overdispersion is identified. In addition, we will assess which secondary outcomes seem to have meaningful discriminatory power in a future study. We will include the potential secondary outcomes that are important and meaningful discriminatory

power in the future study. In addition, we will use the information we obtain in the pilot RCT to conduct sample size estimation for the later trial.

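### The primary partner-testing model states no index-clustered variance, so its 95% intervals are likely too narrow; the adjustment wording beside it needs a small edit

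*Combined protocol and SAP*

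**What the plan says.** For partner testing within 3 months, one of the primary outcomes, the Statistical Analysis Plan uses log-binomial regression to obtain "95% confidence intervals for the proportion of notifiable partners visiting by arm", with risk differences and risk ratios from the same models. It states no variance method. Table 1, which covers the secondary outcomes only, gives "Binomial regression, robust variance" for each partner-level proportion and also names robust variance for each count per index. It does not say what the clusters are.

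Randomisation is by index participant, 80 to intervention and 40 to control. The outcome is counted over partners, and the Randomization section notes that the number of partners varies between index participants.

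On covariates, the plan says that "adjustment for covariates would be necessary if the two study arms are not balanced". The sentence after it, which belongs to the secondary tier and attaches no condition, reads: "we will adjust for pre-specified potential confounding variables that might bias the estimate if not accounted for (e.g. index age, index marital status".

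**The concern.** Partners of one index participant share that person's willingness to notify, his choice of channel and his circle. Their testing outcomes are therefore unlikely to be independent. A binomial model with its default standard error treats each partner as a separate randomised unit. If outcomes are positively correlated within index, it claims more information than the trial holds and its intervals are too short. These are the intervals for the trial's only between-arm primary outcome. The plan also says that "we will use the information we obtain in the pilot RCT to conduct sample size estimation for the later trial", so understated uncertainty could be carried forward.

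The covariate wording is a smaller matter. One sentence makes adjustment depend on imbalance and the next makes it unconditional and secondary, and neither says outright which estimate leads.

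**Working it through.** **1. The plan's own figure.** Sample size and power gives a minimal detectable difference of 26.7 points for 80 versus 40, a 30% control rate, alpha 0.05 and power 0.80. Check 30% against 56.7%, two-sided:
- Pooled proportion: (40×0.30 + 80×0.567)/120 = 0.478.
- Null SE: √[0.478×0.522×(1/40+1/80)] = 0.0967.
- Alternative SE: √[0.30×0.70/40 + 0.567×0.433/80] = 0.0912.
- z = (0.267 − 1.96×0.0967)/0.0912 = 0.85, which gives power 0.80.

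The figure reproduces. It counts each index participant as one observation, so it neither includes nor tests the partner-level analysis.

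**2. Why the default SE is too small.** With m partners per index and within-index correlation ρ, the variance of a partner-level proportion is inflated by D = 1 + (E[m²]/E[m] − 1)ρ. The chance that a nominal 95% interval excludes zero under the null is then about 2[1 − Φ(1.96/√D)].

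**3. Inputs.**
- From the documents: 80 and 40 index participants; 30% testing rate, taken for both arms under the null.
- Assumed: partners per index = max(1, Bernoulli 0.6 + negative binomial with mean 2 and size 1).
- This gives E[m] = 2.6 + 0.4/3 = 2.73, hence 120×2.73 = 328 partners.
- It also gives E[m²] = 6.24 + 2.6² + 0.4/3 = 13.13, so E[m²]/E[m] = 4.80.
- Assumed: normal variation between index participants on the logit scale, with SD 0.6, 1.0 or 1.5. Numerical integration at a 30% mean gives ρ = 0.067, 0.157 and 0.274.

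**4. Results.** The default SE of the risk difference is √[0.21/218.7 + 0.21/109.3] = 5.4 points, a half-width of 10.5 points.

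| Index SD (logit) | D | √D | Half-width needed (10.5×√D) | Null exclusion, formula | Null exclusion, simulated, default SE |
|---|---|---|---|---|---|
| 0.6 | 1 + 3.80×0.067 = 1.26 | 1.12 | 11.8 | 8.0% | 8.6% |
| 1.0 | 1 + 3.80×0.157 = 1.60 | 1.26 | 13.3 | 12.1% | 12.7% |
| 1.5 | 1 + 3.80×0.274 = 2.04 | 1.43 | 15.0 | 17.0% | 17.4% |

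With index-clustered SE the simulated rate is about 6%. A separate simulation at SD 0.6 added age and marital status as null, moderate or strong predictors of testing. It gave 7.9%, 9.1% and 9.9% with the default SE, against 5.7%, 6.3% and 6.1% clustered.

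**5. Range.** If every index had one partner, D = 1 and nothing is lost. At SD 0.6 with equal numbers of partners (2.73 each), D = 1 + 1.73×0.067 = 1.12 and the rate is about 6.4%.

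**6. Robust variance must name the cluster.** In a by-arm model with M partners and proportion p tested, the squared residuals sum to Mp(1−p)² + M(1−p)p² = Mp(1−p). A sandwich estimator that treats partners as independent therefore returns the default variance. Only clustering by index changes it.

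**7. The covariate wording.** In the same simulations the unadjusted and adjusted risk differences (index age, marital status) differ by a median of 0.5 to 1.6 points, against a sampling SD of 6.0 to 6.3 points. Mechanically following an imbalance rule gives null exclusion of 5.7-6.8%, close to the 5.7-6.3% of always using the unadjusted model.

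**The case against.** **The missing phrase may be a drafting gap.** Table 1 shows that the authors had robust variance in mind and may have meant it here too. That cannot be excluded, but Table 1 is limited to secondary outcomes, and an analyst following the text for partner testing would use the default SE.

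**This is a pilot.** The plan says that "the sample size of this study is not designed and will be not powered enough to test the difference between the two arms", and it plans intervals, not a test. This stands, and it limits the consequence. It does not excuse intervals with the wrong coverage, since the interval is the stated product.

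**The sizes rest on invented inputs, and the simulations used logistic models.** The first part stands: the documents give neither partners per index nor clustering. The second matters little for the unadjusted comparison, because with arm as the only term, logistic and log-binomial models fit the same two proportions.

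**A stronger reading of the covariate wording.** A reader might infer that the undefined imbalance condition and the list of examples let the analysts switch to whichever estimate they prefer, perhaps drawing on other variables collected ("socio-demographics, sexual orientation, sexual orientation disclosure status, HIV and other STDs testing history and HIV PS history"). The documents do not support this. They place adjustment in secondary analyses, without condition, and call the variables pre-specified. Nothing links the additional measures to the adjustment. The imbalance sentence can be read as the rationale for the one after it. Chance imbalance also does not bias a randomised comparison on average. What remains is that the list is not printed in full and that the two sentences do not fit together.

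**Conclusion.** The concern holds for the variance of the primary partner-testing model. As written, the 95% intervals are too short whenever index participants with several partners differ in their partners' testing rates. Under the assumed partner distribution, null exclusion of zero is about 8-10% at modest between-index variation and 12.7% or 17.4% at the two stronger settings, against about 6% with index-clustered SE. The direction needs only positive within-index correlation and more than one partner for some index participants; the size depends on assumptions that the documents cannot settle. The point estimates are unaffected.

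The adjustment sentences are a minor matter of wording. The natural reading is that the unadjusted by-arm estimate leads, and the text should say so.

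**What to change.** - In the Statistical Analysis Plan, add to the partner-testing model that variance is robust and clustered by index participant, for the unadjusted and adjusted analyses alike.
- Name the same cluster for the partner-level rows of Table 1.
- In the covariate text, delete the imbalance condition. State that the unadjusted by-arm estimate leads, and that the analysis adjusted for index age and index marital status is always reported beside it.

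The cost is a few words and one option in the analysis program. Partners are already linked to index participants by unique ID or matching, so the cluster variable exists. Age and marital status need no new data item provided the baseline socio-demographic questions include them. Intervals will be wider, by about 12% at the weakest assumed clustering (√1.26 = 1.12) and 43% at the strongest (√2.04 = 1.43). The gain in precision from adjustment may be small or nil. The changes should be made before outcome data are seen by arm.

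### Table 1's robust variance names no cluster unit, small-sample correction or reference distribution; with 40 control index men, its intervals are likely to be modestly too narrow in most rows

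*Combined protocol and SAP*

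**What the plan says.** Table 1 (Statistical Analysis Plan) lists six secondary outcomes, numbered here in table order.

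- Rows 1, 3, 5 and 6 are proportions of partners: notified; HIV-positive among tested; tested among casual; condom use among presenting. Each is assigned "Binomial regression, robust variance".
- Rows 2 and 4 are means per index man: partners tested, and partners with HIV. Both get a count model with robust variance. The text below the table adds: "For count variables expressed as the mean number of partners, we will use either Poisson regression or negative binomial regression if overdispersion is identified".

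Neither place names the cluster unit, a small-sample correction or a reference distribution. The 95% level is stated only for the primary testing outcome; it is assumed here to apply to Table 1 too.

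Index men are the randomised units: "80 for intervention arm and 40 for the control arm, respectively" (Sample size and power). The Randomization section expects some difference in partner totals between arms, "as the number of partners of the index participants is variable". Sample size and power also states that the pilot is not powered for the between-arm comparison.

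**The concern.** The ordinary sandwich variance is justified when there are many independent units. Here partners are nested within index men, so what counts is the number of men and how unequally partners are spread over them. Control has 40 men at most. Rows 3, 5 and 6 use only those with at least one tested, casual or presenting partner. With few, unequal units the fitted proportion is pulled towards the men with most partners, their residuals come out too small, and so does the variance. Normal quantiles add to the shortfall.

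The pilot is meant to show which secondary outcomes could discriminate between arms in the full trial, and to supply inputs for its sample size. Intervals that are too narrow make chance differences look more convincing than they are. The two HIV-positive rows have a separate problem: very few control events, where a ratio behaves badly or does not exist.

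**Working it through.** **The plan's own figure.** The documents state no coverage figure. The one calculation they give, with "alpha=0.05, power=0.80" and a 30% control return rate, is that "the minimal detectable effect size would be 26.7% for this pilot study". For 40 against 80 and 30.0% against 56.7%:

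- pooled p = (40×0.300 + 80×0.567)/120 = 0.478
- null SE = √[0.478×0.522×(1/40 + 1/80)] = 0.0967
- alternative SE = √[0.300×0.700/40 + 0.567×0.433/80] = 0.0912
- z = (0.267 − 1.96×0.0967)/0.0912 = 0.85, so power is 80.2%

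The figure reproduces (two-sided, pooled) with 40 and 80 as the numbers of independent observations.

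**Contributing control men.** At a 30% return rate with independent partners, the expected number with at least one presenting partner is 40×(1 − 0.7^m). That gives 12, 20 and 26 men for m = 1, 2 and 3 partners each. The documents give no value for m.

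**Why the variance is too small.** In an arm-only log-link model, the cluster sandwich for log p̂ is Σ(yᵢ − p̂nᵢ)²/(Σyᵢ)², where man i has nᵢ partners, N in total.

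- With k men of equal nᵢ, its numerator averages (k − 1)/k of the true value. The SE is then short by the factor √(39/40) = 0.987 at k = 40, √(19/20) = 0.975 at 20 and √(11/12) = 0.957 at 12.
- Skew adds to this. With a mean of 4 partners, N = 160. A man with 20 of them has nᵢ/N = 0.125, and the Mancl-DeRouen correction multiplies his residual by 1/(1 − 0.125) = 1.14.

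**Simulated coverage (%) of nominal 95% intervals.** Beta-binomial outcomes within man, 40 against 80 men, ICC 0.1 and 0.3, sandwich clustered on index, uncorrected, z = 1.96. Assumed: half of partners casual; 15% or 40% outcome rate in rows 3 and 6; 15% positivity in row 4. RD = risk difference, RR = risk ratio.

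| Row | Control men | Constant 3 | 1+Poisson, mean 3 | Skewed, mean 4 | Very skewed, mean 6 | Mancl-DeRouen + t (RD), all four |
|---|---|---|---|---|---|---|
| 1 notified (RD, RR) | 40 | 94.2–94.5 | 93.7–94.4 | 92.3–93.1 | 90.8–91.7 | 93.8–95.0 |
| 5 casual (RD, RR) | 28–31 | 93.7–94.7 | 93.6–95.0 | 91.7–93.0 | 89.2–91.8 | 94.2–95.5 |
| 3, 6 (RD) | 20–25 | 92.1–93.9 | 91.7–93.5 | 90.6–92.3 | 89.0–91.3 | 93.3–95.3 |
| 3, 6 (RR) | 20–25 | 94.6–96.4 | 94.0–95.9 | 92.5–94.6 | 89.6–92.7 | not run |
| 2 tested per index (ratio) | 40 | 94.5–94.7 | 94.4–94.6 | 92.4–93.3 | 90.9–91.7 | not run |
| 4 HIV per index (ratio) | 40 | 96.3–96.5 | 95.9–96.2 | 93.4–94.5 | 89.5–92.4 | not run |

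Other runs agree. For row 1 at 30% against 45%, ICC 0.1 to 0.5, RR scale, coverage was 93.6 to 94.5% with mean 2 to 4 and SD 1.4 to 3, and 91.8 to 93.2% at mean 5, SD 6. Casual-partner scenarios with 24 to 32 contributing control men gave 89.4 to 93.9% uncorrected and 93.1 to 95.4% corrected. Forcing only 16 control men with skewed counts gave 85.2 to 91.8%. For row 2, a corrected variance with t gave 93 to 95%.

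**If the variance is not clustered on index.** Coverage of the partner-level rows would be about 79 to 94% with constant or mildly variable counts, and about 46 to 90% with skewed counts.

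**Control events for rows 3 and 4.** With an assumed 3 partners per man, 40×3×0.30 = 36 tested control partners. Positivity of 8%, 15% or 20% gives 2.9, 5.4 or 7.2 positives. Simulated with SD 2.5 and ICC 0.3, control had none in 10%, 1.6% and 0.4% of trials respectively. The 8% is the Chinese MSM prevalence in the Background; the other two are assumptions.

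**The case against.** The strongest reply is that the loss is small, the inputs are assumed, and the setting is forgiving. Much of that stands. With constant or mildly variable partner numbers and 40 control men, coverage is about 93 to 95%. On the ratio scale, rows 3 and 4 often reach 94 to 96% or more. Table 1 does not say that its variance is uncorrected or that normal quantiles will be used; it is silent. These are secondary outcomes of a declared pilot.

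A reader might infer more than the documents support:

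- That 16 to 32 control men feed the restricted rows and that Table 1 intervals cover 89 to 94%. Neither range is in the documents; both depend on partner skew, ICC, casual share and return pattern, none of which is given.
- That these intervals will decide which outcomes go into the full trial. The text after Table 1 promises only an assessment of which outcomes seem to discriminate, with no interval, p-value or threshold.
- That the case-finding ratio will probably not be estimable. That rests mainly on 8% positivity, a general-population MSM figure applied to partners of newly diagnosed men. At 15 to 20% the risk is under 2% in the scenario simulated.

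The reply does not remove the point. Low power does not excuse understated uncertainty, since describing uncertainty is much of what a pilot is for. The plan's silence also leaves the choice open until the data are seen.

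**Conclusion.** The point holds as a modest, conditional one. If the robust variance is clustered on index but uncorrected and paired with normal quantiles, nominal 95% intervals for the notification and casual-partner rows cover about 92 to 95% for mean 2 to 5 partners, SD 1.4 to 6 and ICC 0.1 to 0.5. The usual loss is 1 to 3 points. Values nearer 89 to 90%, or lower in the 16-man stress case, need strong skew or few contributing men. Rows 3 and 4 may over-cover on the ratio scale. Row 4 has no finite ratio when control has no positive partner, and the same is true of row 3 if it is reported as a ratio.

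For the four partner-level rows, the unstated cluster unit matters more than the small-sample bias, so the same sentence should settle both. Severity is low to moderate: a cheap improvement, not a threat to the pilot's main aims.

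**What to change.** Amend Table 1 and the sentence below it:

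1. Proportion rows (1, 3, 5, 6): replace the robust-variance entry with *variance clustered on index participant, with a small-sample correction (e.g. Mancl-DeRouen or Kauermann-Carroll) and a t reference*. Either correction will do: on the risk-difference scale, with t, coverage was about 93 to 95.5% for the first and 92 to 95% for the second.
2. Count rows (2, 4): use a small-sample-corrected robust variance with t. A re-randomisation test is an optional check and must follow the actual allocation scheme, of which the Randomization section gives only the 2:1 ratio. Its error rate was checked for row 2 only (4.6% and 4.1% in two scenarios), not for row 4 or for intervals.
3. Row 4: also report the difference in mean partners with HIV per index man, which stays defined if control has none.
4. State the confidence level for Table 1, and report the number of contributing index men per arm in each row.

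Cost: SAP wording and a standard software option, with no new data. Intervals become about 5 to 10% wider in most scenarios, and somewhat more with strong skew.
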